2.1.1 General definitions

Investigational treatment and study treatment

Investigational treatment, will refer to the ruxolitinib only, while *other study treatment* will refer to concomitant use of corticosteroids to treat treatment-naive cGvHD or SR-cGvHD.

Study treatment, will include both *Investigational treatment* and *other study treatment*.

Date of first administration of study treatment

The date of first administration of study treatment is derived as the first date when a nonzero dose of ruxolitinib was administered as per the DAR eCRF. The date of first administration of study treatment will also be referred as *start of study treatment*.

Date of last administration of study treatment

The date of last administration of study treatment is defined as the last date when a nonzero dose of ruxolitinib was administered as per DAR eCRF. The date of last administration of study treatment will also be referred as *end of study treatment*.

Study day

The study day, describes the day of the event or assessment date, relative to the reference start date.

The study day is defined as:

- The date of the event (visit date, onset date of an event, assessment date etc.) – reference start date + 1 if event is on or after the reference start date;
- The date of the event (visit date, onset date of an event, assessment date etc.) – reference start date if event precedes the reference start date.

The reference start date for all assessments (e.g. safety, efficacy, PK, biomarker, etc.) is the start of study treatment.

The study day will be displayed in the data listings. If an event starts before the reference start date, the study day displayed on the listing will be negative.

Time unit

A year length is defined as 365.25 days. A month length is 30.4375 days (365.25/12). If duration is reported in months, duration in days will be divided by 30.4375. If duration is reported in years, duration in days will be divided by 365.25.

Baseline

For safety and efficacy evaluations, the last available assessment on or before the date of start of study treatment is defined as “baseline” assessment.

If patients have no value as defined above, the baseline result will be missing.

On-treatment assessment/event and observation periods for safety analyses

The overall observation period will be divided into three mutually exclusive segments:

1. ***pre-treatment period***: from day of patient's informed consent to the day before first administration of ruxolitinib.
2. On-treatment period: from day of first dose of ruxolitinib to 30 days after date of last actual administration of assigned treatment.
3. ***post-treatment period***: starting at Day 31 after last administration of ruxolitinib.

Safety summaries (tables, figures) include only data from the on-treatment period with the exception of baseline data which will also be summarized where appropriate (e.g. change from baseline summaries). In addition, a separate summary for death including on-treatment and post-treatment deaths will be provided. In particular, summary tables for adverse events (AEs) will summarize only on-treatment events, with a start date during the on-treatment period (***treatment-emergent*** AEs).

However, all safety data (including those from the post-treatment period) will be listed and those collected during the pre-treatment and post-treatment period will be flagged. In analyses for the safety disclosure, all AEs collected in the post-treatment period will be included and reported separately.

Subjects who taper off ruxolitinib due to achieving a CR or PR continue efficacy and safety assessments until their EoT visit which may be only after Cycle 39 unless the subject discontinues from study earlier. Safety data from these patients collected after the last study drug intake date + 30 days and before EoT visit will not be included in any safety analyses based on the on-treatment period as defined above. Nevertheless, these data will be listed and flagged in all listings (AEs, lab, vital signs). Subject who tapered off ruxolitinib are identified as they have reason "responder" for ruxolitinib permanent discontinuation on the exposure CRF.

For subjects who tapered off study treatment and later re-started ruxolitinib treatment after a cGvHD recurrence, the on-treatment period is from date of first dose of ruxolitinib to very last dose + 30 days including the period without treatment, which are collected in the database as dose interruption. Safety data (e.g. AEs, labs) collected during this period without treatment will be included in the summary tables as treatment emergent events.

Windows for multiple assessments

In order to summarize data collected over time (including unscheduled visits), the assessments will be time slotted. The following general rule will be applied in creating the assessment windows: If more than one assessment is done within the same time window, the assessment performed closest to the target date will be used. If two assessments within a time window are equidistant from the target date, then the earlier of the two assessments will be used. If multiple assessments on the same date then the worst case will be used. Data from all assessments (scheduled and unscheduled), including multiple assessments, will be listed.

The following time windows are defined for descriptive summary on cGvHD assessment, biomarkers, and safety (Table 2-1) by visit. The end of treatment assessment will be mapped into the time points as needed.

Table 2-1 Time windows for cGvHD assessment and safety assessment (lab, vital sign, etc.)

Time Window	Planned Visit Timing	Time Window Definition
On treatment		
Baseline	On or before Study Day 1	≤ Study Day 1
Cycle 1 Day 8	Study Day 8	Study Days 5 – 11
Cycle 1 Day 15	Study Day 15	Study Days 12 – 18
Cycle 1 Day 22	Study Day 22	Study Days 19 – 25
Cycle 2 Day 1	Study Day 29	Study Days 26 – 39
Cycle 3 Day 1	Study Day 57	Study Days 47 – 67
Cycle 4 Day 1	Study Day 85	Study Days 75 – 95
Cycle 5 Day 1	Study Day 113	Study Days 103 – 123
Cycle 6 Day 1	Study Day 141	Study Days 131 – 151
Cycle 7 Day 1	Study Day 169	Study Days 159 – 179
Cycle 9 Day 1	Study Day 225	Study Days 211 – 239
Cycle 12 Day 1	Study Day 309	Study Days 295 – 323
every 12 weeks	+ 84 day	+84 days to lower and upper bound
Cycle 39 Day 1	Study Day 1065	Study Days 1051 – 1179
Safety follow-up	30 days after last dose	Last dose date + 30
Study Day 1 = start date of study treatment; EOT assessments are mapped to the time points as needed.		

Last contact date

The last contact date will be derived for patients not known to have died at the analysis cut-off using the last complete date among the following:

Table 2-2 Last contact date data sources

Source data	Conditions
Last contact date/last date patient was known to be alive from Survival Follow-up page	Patient status is reported to be alive, lost to follow-up or unknown.
Start/End dates from new cGvHD treatment since discontinuation from study treatment	Non-missing medication/procedure term.
Start/End* dates from drug administration record/concomitant medication record	Non-missing dose. Doses of 0 are allowed.
Date of discontinuation from end of treatment pages	No condition.
- cGvHD assessment date	Non-missing assessment.

Source data	Conditions
- any specific efficacy assessment date if available (e.g. graft failure assessment, hematologic disease relapse/progression assessment)	
Laboratory/PK collection dates/Biomarker collection dates	Sample collection marked as 'done'.
Vital signs date	At least one non-missing parameter value.
Assessment date of development information (e.g. tanner staging)	Evaluation is marked as 'done'.
Collection date of acceptability and palatability questionnaire	Assessment performed is "Yes".
Start/End dates of AE	Non-missing verbatim term

The last contact date is defined as the latest complete date from the above list on or before the data cut-off date. The cut-off date will not be used for last contact date, unless the patient was seen or contacted on that date. No date post cut-off date will be used. Completely imputed dates (e.g. the analysis cut-off date programmatically imputed to replace the missing end date of a dose administration record) will not be used to derive the last contact date. Partial date imputation is allowed for event (death)/censoring if coming from 'Survival information' eCRF.

The last contact date will be used for censoring of patients in the analysis of overall survival, failure free survival, non-relapse mortality, and malignancy relapse/recurrence.

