2.4 Treatments (study treatment, rescue medication, concomitant therapies, compliance)

2.4.1 Study treatment / compliance

Duration of exposure to ruxolitinib will be summarized by Age group and by means of descriptive statistics. It will also be categorized into time intervals; frequency counts and percentages will be presented for the number (%) of patients in each interval.

Total daily dose, actual cumulative dose, dose intensity (DI) and relative dose intensity (RDI) will be summarized for ruxolitinib by Age group.

The number (%) of patients who have dose reductions or interruptions, and the reasons, will be summarized for ruxolitinib by Age group.

Patient level listings of all doses administered on treatment along with dose change reasons will be produced by Age group.

The Safety Set will be used for all summaries and listings of study treatment.

If more than one dose and/or formulation is assigned within one Age group, then summaries and listings will be reported by Age group as well as doses/formulation within the Age group

Duration of follow-up

The duration of follow-up time is defined as (date of last contact) – (date of first administration of investigational treatment) + 1.

Duration of exposure to investigational treatment

Duration of exposure to investigational treatment (days) = (last date of exposure to investigational treatment) – (date of first administration of investigational treatment) + 1.

If any subjects tapered off ruxolitinib and re-started ruxolitinib treatment due to cGvHD recurrence, two different definitions of duration of exposure will be distinguished:

- **Duration of exposure including taper off periods** is defined as the time from first to very last date of ruxolitinib treatment, which includes the intervening period without treatment.
- **Duration of exposure excluding taper off periods** is defined as above but deduct the intervening period without treatment for subjects who taper off and restart after cGvHD recurrence. These periods are captured as dose interruption with reason “dose tapering following response”.

Summary of duration of exposure of investigational treatment in days will include categorical summaries (based on clinically meaningful time intervals) and continuous summaries (i.e. mean, standard deviation etc.) using appropriate units of time.

Duration of exposure to investigational treatment in patient-years

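### Off-drug events more than 30 days after taper-off count as treatment-emergent only if the child later restarts ruxolitinib

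*SAP*

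**What the plan says.** The general rule in SAP 2.1.1, which matches Protocol 12.5.2, runs the on-treatment period from the first dose of ruxolitinib "to 30 days after date of last actual administration of assigned treatment". Being treatment-emergent is purely a matter of dates: "summary tables for adverse events (AEs) will summarize only on-treatment events, with a start date during the on-treatment period".

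SAP 2.1.1 then adds two paragraphs on responders who taper off.

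- **No restart.** These subjects "continue efficacy and safety assessments until their EoT visit which may be only after Cycle 39", so off-drug safety data exist. However: "Safety data from these patients collected after the last study drug intake date + 30 days and before EoT visit will not be included" in on-treatment analyses. They are listed and flagged.
- **Restart after recurrence.** Here "the on-treatment period is from date of first dose of ruxolitinib to very last dose + 30 days including the period without treatment". The drug-free interval is stored as a dose interruption, and AEs and laboratory data "collected during this period without treatment will be included in the summary tables as treatment emergent events".

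Protocol 6.1.5 leaves treatment of a recurrence, including whether to restart ruxolitinib, to the investigator. The SAP gives no reason for handling the two groups differently.

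**The concern.** Take two children who stop ruxolitinib on the same day after a response and follow the same visit schedule. Each has the same event on the same off-drug day. If one later recurs and restarts, that child's event enters the treatment-emergent tables. The other child's does not. The class of an event already observed is fixed by something that happens afterwards, and that something is itself an outcome (recurrence) followed by a discretionary decision.

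Three consequences follow.

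- The off-drug experience in the main safety tables comes only from children who recurred and restarted.
- A death more than 30 days into the drug-free period can never be on-treatment, because a restart requires survival.
- An event can change class between the interim and final reports if the child restarts between the two cut-offs.

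**Working it through.** The plan states no figure on this point, so there is none to reproduce. The check applies the SAP rule to two subjects whose histories are identical up to the event.

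**Inputs from the documents**
- Treatment-emergent if first dose ≤ event start ≤ last dose + 30 days. For a restarter, the last dose is the very last one (SAP 2.1.1).
- Ruxolitinib taper is possible from Cycle 7 Day 1 (Protocol 6.1.5), which is Study Day 169 (SAP Table 2-1).
- Taper steps are about 56 days (Protocol 6.1.5.2).
- The planned course is 39 cycles of 28 days: 39 × 28 = Day 1092.
- 46 subjects were enrolled (Protocol, Amendment 2).

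**Assumptions for illustration**
- Two 56-day steps from Day 169, so drug stops at 169 + 56 + 56 = Day 281. This is near the fastest route, since Protocol 6.1.5.2 also requires the child to be off corticosteroids and CNIs first.
- In the restarter, the very last dose is on Day 700.

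**Classification**
- Without restart, on-treatment ends on 281 + 30 = Day 311.
- With restart, it ends on 700 + 30 = Day 730.

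| Event start | No restart | Later restart |
|---|---|---|
| Day 301 (20 days off drug) | treatment-emergent | treatment-emergent |
| Day 312 (31 days off drug) | not | treatment-emergent |
| Day 400 (119 days off drug) | not | treatment-emergent |

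The first 30 drug-free days are on-treatment for everyone, so the split concerns only the time beyond them. With these dates, the ceiling on off-drug follow-up that could be classed either way is 1092 − 311 = 781 days. As a second assumed case, stopping at month 9 and restarting at month 27 gives 18 × 30.4375 ≈ 548 drug-free days, of which about 548 − 30 = 518 would be classed differently.

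**Chance that one restarter gains at least one extra treatment-emergent event.** With a constant AE rate r per year, this is 1 − exp(−r × (gap − 30)/365.25). Both the rates and the gap lengths are assumed; the documents give neither.

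| Gap | Days beyond 30 | r = 0.5 | r = 1 | r = 2 |
|---|---|---|---|---|
| 90 days | 60 | 7.9% | 15.1% | 28.0% |
| 180 days | 150 | 18.6% | 33.7% | 56.0% |

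**Where the period is used**
- SAP 2.8.1: AE tables cover on-treatment events.
- SAP 2.8.3: laboratory shift tables take the worst on-treatment value.
- SAP 2.8.4.2 and 2.8.4.5: vital-sign summaries and growth shift tables use on-treatment values.
- SAP 2.8.4.3: for grade 3 or higher infection, the end of the on-treatment period is a competing-risk date. A first such infection on Day 400 is an event for the restarter. For the non-restarter it falls after a competing event on Day 311.

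**The case against.** The best defence is that there is only one rule, last dose plus 30 days, and that a restarter simply has a later last dose. The SAP discloses this openly, and it adds events to the main table, which can pass as cautious in a descriptive single-arm study. The first part is fair: the restart paragraph spells out a property that the general rule already has. It does not make the result consistent. The rule is inclusive for restarters and exclusive for every other tapered responder, so it is not uniformly cautious.

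Three stronger readings are tempting, and the documents do not support them.

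- **That event and exposure periods mismatch.** SAP 2.4.1 also defines an exposure duration that "is defined as above but deduct the intervening period without treatment", and uses it as the dose-intensity denominator. But the same section defines a duration that includes the gap, and SAP 2.8.1 reports numbers and percentages of patients. No exposure-adjusted AE rate is planned, so no specified AE estimate is affected.
- **That non-restarters' later events are lost.** They are listed and flagged. Post-treatment events are reported separately in the disclosure tables (SAP 2.8.1.1), and all deaths are summarised (SAP 2.8.2). What remains is that the disclosure tables use the same period definitions, so restarters' gap events are on-treatment there too.
- **That off-drug events are blamed on ruxolitinib.** Treatment-emergent is a timing label. Causality is the investigator's separate assessment (Protocol 10.1.1), and related events have their own tables.

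**Conclusion.** The point stands as an inconsistency in how off-drug time is classed. Beyond 30 days after taper-off, the treatment-emergent status of an event depends on whether the child later restarts. This follows directly from the SAP text and needs no assumption.

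The size does rest on assumptions. Only restarters' data are classed differently, and only for gaps longer than 30 days. The number of restarters is not stated, and the study enrolled 46 subjects in all. The calendar dates, AE rates and gap lengths used above are illustrative. A material distortion of the safety tables is therefore not shown, and the effect may be small. No efficacy conclusion is affected. This is a cheap improvement, not a flaw that threatens the study.

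**What to change.** Define on-treatment by ruxolitinib episode: from the first dose of each episode to the last dose of that episode plus 30 days. Split episodes only at interruptions recorded as tapering after response (SAP 2.4.1), so that interruptions for toxicity stay on-treatment as now. For children who do not restart, the episode ends at the discontinuation recorded with the responder reason. Put the off-drug events of restarters and non-restarters together in one off-treatment table.

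For time to first grade 3 or higher infection, state whether follow-up ends at the first episode plus 30 days for everyone. If it does, first infections in a later episode leave that curve and should be tabulated.

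If the current main definition is kept, add the episode-based version as a sensitivity summary for AEs, laboratory data and grade 3 or higher infections, and report the number of restarters and their gap lengths.

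The cost is SAP wording and one derivation from records already collected. The downside is that a few AEs move from the main table to the off-treatment table.

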8.2.1 Treatment Period

The treatment period will begin on Cycle 1 Day 1, which is the baseline disease assessment visit. The primary efficacy endpoint assessment will be conducted on Cycle 7 Day 1 of the treatment period, with a window of +/- 7 days. The total duration on study for an individual subject will be 39 Cycles (156 weeks or approximately 36 months), inclusive of the treatment period and safety follow-up. Each cycle is a total of 28 days.

Study visits will occur at the following frequency in the treatment period, as specified in [Table 8-1](#):

[figure not shown]
- Cycle 1 Day 1
- Every week in Cycle 1 (Day 8, 15, 22) (+/- 3 days)
- Every 4 weeks from Cycle 2 Day 1 until Cycle 7 Day 1 (+/- 7 days)
- Next visit after Cycle 7 Day 1 is Cycle 9 Day 1 (+/- 7 days)
- Every 12 weeks from Cycle 9 Day 1 until Cycle 39 Day 1 (+/- 14 days)

The End of Treatment (EOT) visit is completed when a subject completes 39 cycles of the treatment period, **or** if a subject permanently discontinues ruxolitinib early.

All subjects must complete a safety follow-up visit, 30 days (+3 days) from the last dose of ruxolitinib.

If a subject permanently discontinues ruxolitinib early, after completing the EOT **and** safety follow-up visit, he/she should follow the early discontinued follow-up schedule as specified in [Table 8-1](#). Visits should occur every 6 months (+/- 14 days) until the subject reaches 3 years from the time of first dose of ruxolitinib.

Refer to [Figure 8-1](#).

Figure 8-1 Study Treatment Period

Unscheduled visits may be performed as necessary.

A more frequent schedule of assessments is recommended for dose tapering, dose modifications, or as clinically indicated. Additional assessments may be performed as per institutional guidelines, as per the investigator's discretion, or as per the label. Chronic GvHD assessments performed at an unscheduled visit and leading to a change in the subject's management, or during the treatment period leading to a change in the subject's response, should be recorded in the eCRF, as well as any other relevant assessment performed.

For details on the schedule of assessments, see [Table 8-1](#).

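### The Cycle 39 Day 1 analysis window in SAP Table 2-1 ends at Study Day 1179; the table's own rule and the protocol's visit tolerance both give 1079.

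*SAP*

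**What the plan says.** SAP section 2.1.1, Table 2-1, defines the windows that place assessments, including unscheduled ones, at nominal visits for descriptive by-visit summaries.

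- Cycle 9 Day 1 (target 225) has the window "Study Days 211 – 239" and Cycle 12 Day 1 (target 309) has "Study Days 295 – 323".
- For later 12-weekly visits the target moves on by 84 days, and the window row says to add "84 days to lower and upper bound".
- The Cycle 39 Day 1 row then gives the target as "Study Day 1065" and the window as "Study Days 1051 – 1179".
- The next row is the safety follow-up, placed at the last dose date plus 30 days.

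The tie rule is: "If more than one assessment is done within the same time window, the assessment performed closest to the target date will be used". The section also says that EOT assessments are assigned to the visit time points where needed, without stating a rule.

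Protocol section 8.2.1 schedules the later visits as "Every 12 weeks from Cycle 9 Day 1 until Cycle 39 Day 1 (+/- 14 days") and fixes the cycle length: "Each cycle is a total of 28 days".

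**The concern.** The Cycle 39 row disagrees with the row directly above it. One programmer might build the later windows by recursion and another might type in the printed bound, and they would get different data sets for the last visit. The printed window reaches past the planned end of Cycle 39. It takes in the EOT visit and overlaps the separate safety follow-up row. A subject who missed the Cycle 39 visit could then have a later value reported as Cycle 39 Day 1.

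At stake are the by-visit descriptions at the end of the study: cGvHD assessments, vital signs, laboratory time courses, and the 6-monthly growth summaries, which take their height and weight values from Table 2-1 (SAP section 2.8.4.5).

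**Working it through.** **Inputs.** Cycle length 28 days and visit tolerance ±14 days (protocol section 8.2.1). Cycle 12 target 309 and window 295–323, step of 84 days, Cycle 39 target 1065 and window 1051–1179 (SAP Table 2-1). EOT visit within 7 days of the last dose (protocol Table 8-1). On-treatment period to last dose + 30 days (SAP section 2.1.1).

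**1. Target.** Cycle k Day 1 = 28×(k − 1) + 1. For k = 39: 28×38 + 1 = 1065. The plan's target reproduces.

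**2. Window by the table's own rule.** From Cycle 12 to Cycle 39 there are (39 − 12)/3 = 9 steps.
- Target: 309 + 9×84 = 1065, as printed.
- Lower bound: 295 + 9×84 = 1051, as printed.
- Upper bound: 323 + 9×84 = **1079**, not 1179.

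The last three windows in the sequence are Cycle 33, 883–911; Cycle 36, 967–995; Cycle 39, 1051–1079.

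**3. Window by the protocol tolerance.** 1065 − 14 = 1051 and 1065 + 14 = 1079. This agrees with step 2.

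**4. Size of the discrepancy.**
- Printed minus rule-based upper bound: 1179 − 1079 = 100 days.
- Printed upper bound minus target: 1179 − 1065 = 114 days, against 14.
- Width: 1179 − 1051 + 1 = 129 days, against 1079 − 1051 + 1 = 29.

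**5. What can fall in the extra 100 days.** Assume dosing to the end of Cycle 39 on schedule.
- Last dose: 39×28 = day 1092, which is 27 days after target.
- Latest EOT visit: 1092 + 7 = day 1099, which is 34 days after target.
- End of the on-treatment period: 1092 + 30 = day 1122, which is 57 days after target.

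If Cycle 39 Day 1 itself is 14 days late (day 1079) and dosing runs 28 days from then, the last dose is day 1106 and the on-treatment limit is day 1136, 71 days after target. This case is illustrative. For a safety value at day 1179 to count as on-treatment, the last dose would have to be at day 1179 − 30 = 1149 or later, well after the planned end of dosing at day 1092.

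**The case against.** The strongest defence is that the last window was widened on purpose to catch EOT values, since the SAP says EOT assessments are assigned to visit time points where needed. But no text says that the Cycle 39 window serves this purpose, and no rule in the documents yields 1179. On the planned schedule EOT falls by day 1099, so catching it would not need day 1179. What stands is a practical point: with 1079 alone, an on-schedule completer's EOT value at about day 1092 falls outside every visit window, so the plan must say where it goes.

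The other objections concern size, and they largely stand.

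- A reader might infer that values 114 days after target will be reported as the last on-treatment visit. The closest-to-target rule excludes this for anyone assessed in days 1051–1079, and the last dose + 30 day limit excludes it for safety summaries on the planned schedule.
- A reader might infer that safety follow-up laboratory and vital-sign values would enter. Protocol Table 8-1 schedules no hematology, chemistry, height, weight or vital signs at that visit.
- A reader might infer that this is the only asymmetric window. It is not: Cycle 2 Day 1 (target 29, window 26–39) is −3/+10 days. Its lower bound abuts the Cycle 1 Day 22 window (19–25), so it is not the same kind of slip.
- Many analyses do not use this window. The primary endpoint uses days 159–179. Best overall response, duration of response and corticosteroid-free response do not depend on the Cycle 39 window. The laboratory and growth shift tables use the worst on-treatment value. Biomarkers are in a separate plan.

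**Conclusion.** The upper bound is wrong as written. Two independent routes give 1079, the target and lower bound both reproduce, and the discrepancy is exactly 100 days, which looks like a one-digit slip.

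The consequence is minor. It reaches only subjects with no assessment in days 1051–1079. For them the likely substitute is the EOT value, 27 to 34 days after target. For safety data the reach is about 57 days. For by-visit cGvHD summaries the SAP does not expressly apply the on-treatment limit, and subjects who tapered off ruxolitinib after response continue efficacy assessments until an EOT visit that may come only after Cycle 39. The printed bound is therefore the only stated limit there, although the planned schedule puts nothing near day 1179.

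These figures assume 28-day cycles kept to schedule and dosing through day 1092. The documents do not show how many subjects lack a Cycle 39 assessment in range, so the number affected is unknown. The documents do not support reading this as a threat to the primary endpoint or to the main safety conclusions.

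**What to change.** In SAP Table 2-1, change 1179 to 1079 in the Cycle 39 Day 1 row, and check that the analysis program uses the same bound.

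Decide separately what to do with EOT values. If they are to be summarised by visit, add an EOT row with its own definition in place of the open-ended mapping sentence. If they are not, say that they are listed only. It would also help to state whether the last dose + 30 day limit applies to by-visit cGvHD summaries.

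The window correction costs one number in the SAP and one program check. An EOT row adds one line to the table and a little programming. No new data are needed, and no primary result changes.
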